4.9 Analysis Periods

The following analysis periods will be defined as:

- Pre-Injection Period: from the start day of biopsy to the first REACT injection.
- Acute First Injection Period: from the first REACT injection to 1 month following the first REACT injection. The acute first injection period is a subset of the inter-injection period defined below.
- Inter-Injection Period: from the first REACT injection to either the second REACT injection or (if no such second injection was delivered) trial withdrawal or completion.
- Acute Second Injection Period: from the second REACT injection to 1 month following the second REACT injection. The acute second injection period is a subset of the post-second-injection period defined below.
- Post-Second Injection Period: from the second REACT injection to trial withdrawal or completion. This period will not apply to participants for whom only one REACT injection was delivered.
- Post-Injection Period: from the first REACT injection to trial withdrawal or completion. This period includes both the inter-injection and post-second injection periods.

[figure not shown]
If necessary, imputed dates will be used to determine the analysis period for adverse events.

Figure 1. Analysis Period Diagram for Subjects that Received Two Injections

Abbreviations: EOS = End of Study

Figure 2. Analysis Period Diagram for Subjects that Received One Injection

Abbreviations: EOS = End of Study

5. STUDY SUBJECTS

5.1 Disposition of Subjects

Subject disposition including number of subjects screened, frequency count and proportion of screen failures will be summarized for all screened subjects. Additionally, a summary of enrolled/biopsied, received one or two REACT injections, stage of withdrawal and reason, completed study will be summarized for all screened subjects by presenting frequency counts and the proportion of subjects. A by subject listing of all screened subjects will also be provided.

5.2 Protocol Deviations

Distribution for the types of protocol deviations and the number and percent of subjects that deviate from the protocol will be tabulated using the FAS. A listing of all protocol deviations will be provided.

5.3 Demographic and Screening Characteristics

For the FAS, demographics including age, gender, race, and ethnicity will be summarized using descriptive statistics. Additionally, the following measurements taken at screening will be summarized using descriptive statistics for the FAS: height, weight, BMI, treated kidney cortical thickness, untreated kidney cortical thickness, treated kidney volume, and untreated kidney volume.

Cortical thickness is measured by MRI and ultrasound. For this summary, the screening result for

cortical thickness taken from the MRI assessment will be used, if available. If the MRI assessment is unavailable, the cortical thickness as measured by ultrasound will be used, if available. Volume is measured by MRI and CT scan. For this summary, the screening result for volume taken from the MRI assessment will be used, if available. If the MRI assessment is unavailable, the volume as measured by the CT scan will be used, if available.

If the FAS and IAS are different, then demographics and screening characteristics will be summarized for the IAS as well.

5.4 Medical History

All medical conditions and surgical procedures will be classified by system organ class (SOC) and preferred term (PT) using the Medical Dictionary for Regulatory Activities (MedDRA). The number and percent of subjects with each medical condition and surgical procedure will be presented for each SOC and PT using the FAS. A by-subject listing will also be created.

5.5 Prior and Concomitant Medications

Prior and concomitant medications will be coded using the most recent World Health Organization (WHO) drug dictionary available at the time of analysis. The number and percent of subjects in the FAS using prior and concomitant medications will be tabulated by default Anatomical, Therapeutic, and Chemical (ATC) class level 4 and by generic name. In the case where ATC Level 4 value is not available (i.e. no term per WHO dictionary), the next non-missing lowest ATC level will be used for this summary. For example, if the ATC level 3 value is blank, then the ATC level 2 value will be used. If the ATC level 2 value is blank, the ATC level 1 value will be used. A listing of all prior and concomitant medications recorded in the database will be provided.

Additionally, there are several classes of medications that are of special interest. Separate tables for prior and concomitant medications of special interest will present the number and percentage of subjects in the FAS using medications in the following categories of special interest along with the generic name of the medication. The listing of prior and concomitant medications will identify whether each medication listed meets criteria for inclusion into one of the categories of special interest, and which category the medication falls into. The categories of special interest include: sodium-glucose cotransporter-2 (SGLT2) inhibitors [e.g., dapagliflozin, canagliflozin, empagliflozin], mineralocorticoid receptor antagonists [e.g., finerenone], angiotensin II receptor blockers (ARBs), angiotensin-converting enzyme (ACE) inhibitors, hyperkalemia therapy [e.g., lokelema, kayexalate], sodium bicarbonate, anemia therapy [e.g., epogen], phosphate binders [e.g., PhosLo, renagel], secondary hyperparathyroidism therapy [e.g., calcitrol], and medications to treat edema [e.g., Lasix, bumex].

A prior medication is defined as one which administration ended within 30 days before Biopsy. A concomitant medication is defined as any medication taken after Biopsy.

6. EFFICACY ANALYSIS

6.1 Primary Efficacy Endpoint and Analysis

The primary endpoint of this study is safety related and therefore there is no primary efficacy endpoint.

6.2 Secondary Efficacy Endpoints and Analyses

The secondary efficacy endpoints are renal-specific laboratory assessments including: eGFR as estimated by three CKD-EPI equations [2009 CKD-EPI serum creatinine equation, 2012 CKD-EPI cystatin C equation, and 2012 CKD-EPI serum creatinine-cystatin C equation], random urine albumin to creatinine ratio (UACR), 24 hour urine albumin, 24 hour urine protein, cystatin C, serum creatinine, blood urea nitrogen, bicarbonate, potassium, phosphorus, calcium, intact parathyroid hormone (iPTH), hemoglobin, and hematocrit.

Measurements taken after dialysis has started will be removed from all efficacy analyses.

Listings of lab assessments will include a notation for assessments taken after the start of dialysis so that it is clear which records are included in the efficacy analyses.

Renal-specific lab values will be summarized by presenting descriptive statistics of raw data and change from baseline values at each time point using the IAS.

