## 2. PHASE II TRIAL OBJECTIVES AND PURPOSE

ProKidney is currently developing a regenerative cell-based product, Renal Autologous Cell Therapy (REACT), with the aim of improving renal function in subjects who have CKD and T2DM. Therapeutic intervention with REACT is intended to delay the need for renal replacement therapy (dialysis or transplant) which, based on the current standard-of-care, is inevitable for patients with end-stage CKD. The purpose of the present study is to compare the safety and efficacy of up to 2 injections of REACT given 6 months (+4 weeks) apart (maximum). Each subject's annual rate of renal decline, based on adequate historical clinical data from 24 months prior to the Screening Visit, will serve as a comparator to monitor the rate of progression of renal insufficiency.

We propose that REACT treatment will reduce the rate (slope) of eGFR decline and improve renal function over the 24-month period following the last REACT injection.

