### 8.6. Stopping Rules for an Individual Subject

The Investigator, Medical Monitor, DSMB, and Sponsor may remove any subject from the study for:

- Any clinical AE, laboratory abnormality, intercurrent illness, other medical condition or situation whereby continued participation in the study would not be in the best interest of the subject.
- Development of any exclusion criterion.

If a subject is terminated from the study, EOS assessments should be conducted at the last visit.

If any of the following events occur, no additional subjects can receive REACT injections until review by the DSMB has been completed:

- An SAE that is rated as severe or life-threatening and, in the judgment of the Investigator, is related to REACT or study procedures
- Death of an enrolled subject
- Similar SAE's in more than one subject that are related to REACT, in the judgment of the Investigator
- Inability to deliver a minimum of 50% of the dose of REACT in more than one subject due to surgical or other issues

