4.4 Assessment Windows

No analysis windows are planned for the study regarding data collected outside the protocol specified windows. All data will be included in the analysis based on the visit as it is recorded in the database.

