6.3.4 Rate of Progression of Renal Disease

Using the IAS, the rate of progression of renal disease will be assessed graphically for eGFR as estimated by the 2009 CKD-EPI serum creatinine equation, serum creatinine, and 24 hour urine albumin, and 24 hour urine protein. For each subject a plot of the lab result versus time (in study days) will be displayed, showing vertical lines at biopsy date, 1st and 2nd injection, and the initiation of dialysis, if it is administered. Additionally, for eGFR, the rate of progression of renal disease will be assessed by estimating the annualized eGFR slope over time for each subject. Each subject will serve as his or her own control. The subject's previous medical history, which must include a minimum of 6 months of observation of renal function, will serve as the control for rate of progression of renal insufficiency. The historical eGFR measurements as well as all on study measurements taken prior to the first REACT injection will constitute the pre-injection period for this analysis.

The annualized rate of eGFR decline for the pre-injection, post-second injection, and post-injection periods will be estimated separately by linear mixed effects models. That is, separate models will be fit for each of the specific time periods: pre-injection, post-second injection, and post-injection periods. Each subject with a minimum of 3 observations during the period of interest will be modeled. The model will include unscheduled visits, and only the last measurement if there was a re-test on the same day.

For the pre-injection period, the linear mixed effects model will include eGFR as the dependent variable, and time (in years, derived as study day/365) as the independent variable. To account for between-subject variability in eGFR trajectories, random slopes and intercepts will be included. An unstructured covariance matrix will be used for the model. If the model cannot be fit with the unstructured covariance matrix, the following structure will be tried in the order listed below (decreasing number of parameters) until the one of them fit the model:

1. First-order autoregressive moving average (ARMA(1,1))
2. First-order autoregressive (AR(1))
3. Compound symmetry (CS)
4. Variance Components (VC)

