6.3.5 Time to Dialysis

Using the IAS, the number and percentage of subjects who started dialysis will be reported along with the Kaplan-Meier estimates for the quartiles of the distribution for time to dialysis.

Additionally, a Kaplan-Meier plot and a listing of the derived time to dialysis values will be presented.

Time to dialysis is defined as the time in months from the first REACT injection to the start of dialysis. Subjects who did not start dialysis during the study will be censored as of their last visit date.

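### The efficacy rules in the SAP are triggered by dialysis only, so eGFR measured after a kidney transplant without prior dialysis would stay in the change tables and slope model (minor)

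*SAP*

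**What the plan says.** SAP 6.2 sets one removal rule for efficacy data: "Measurements taken after dialysis has started will be removed from all efficacy analyses". The same rule stands in 6.3.1 (quality of life), 6.3.2 (ultrasound) and 6.3.3 (scintigraphy), with listing flags for records after dialysis. SAP 6.3.4 does not repeat it, but the rule covers every efficacy analysis and so reaches the slope model. The subject plots in 6.3.4 are described as "showing vertical lines at biopsy date, 1st and 2nd injection, and the initiation of dialysis, if it is administered". For time to dialysis, 6.3.5 adds: "Subjects who did not start dialysis during the study will be censored as of their last visit date".

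On which data enter, SAP 4.4 says: "All data will be included in the analysis based on the visit as it is recorded in the database". For the slope, 6.3.4 says: "The model will include unscheduled visits". SAP 4.9 ends the post-injection period at withdrawal or completion.

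Protocol Section 2 describes REACT as "intended to delay the need for renal replacement therapy (dialysis or transplant"). None of the SAP's efficacy rules mentions transplantation, and SAP Section 10, which lists departures from the protocol, does not explain why.

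**The concern.** The protocol names two forms of renal replacement, and the analysis rules act on one. Removing values after dialysis keeps the eGFR results about the subject's own kidneys. A transplant breaks that link in the same way, because the eGFR then largely describes the graft. Values after a transplant that follows dialysis are already removed. The gap is a transplant with no dialysis before it.

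Subjects enter with eGFR 14 to 20, at the boundary of Stages 4 and 5 in Protocol Table 4, and planned participation is 31 months. With at most 10 subjects, and fewer at late visits once post-dialysis values are removed, one graft value carries weight. A failure of native function would be averaged in as a gain. The alternative would be to change the rule after open-label data had been seen.

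**Working it through.** The plan gives no figure to reproduce: there is no powered sample size and no assumed transplant rate. The check is therefore textual, followed by conditional arithmetic.

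**1. Does another passage close the gap?**
- Protocol 8.6 says that the investigator, medical monitor, DSMB and sponsor "may remove any subject from the study for" developing an exclusion criterion. A history of renal transplantation is Exclusion 2. This is a permission, not a requirement.
- Protocol 8.6 also says: "If a subject is terminated from the study, EOS assessments should be conducted at the last visit". A subject who leaves after a transplant can therefore still contribute an end-of-study value. Note d to Protocol Table 1 gives the early and the Month-24 end-of-study visits the same name. How an early visit is coded cannot be seen from the documents.
- The Protocol Synopsis (Study Enrollment) asks sites to make every effort to complete follow-up once a subject is injected.
- SAP 7.3 keeps unscheduled laboratory results out of summary tables, so those values reach the slope model rather than the visit tables.

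Nothing removes the graft values.

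**2. Shift in a visit mean.** Let n subjects have a value at the visit, one of them transplanted with baseline B and graft value G. Let D be the mean change of the other n − 1.
- Kept: [(n − 1)D + (G − B)]/n. Removed: D.
- Difference: [(G − B) − D]/n = (G − N)/n, where N = B + D is the native eGFR the subject would show with the average change.

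The values of G and N are assumed: G 40 to 60, N 8 to 12. That N corresponds to a fall of 5 to 9 from 17, the midpoint of the entry range.
- n = 10: (40 − 12)/10 = +2.8 to (60 − 8)/10 = +5.2.
- n = 6: (40 − 12)/6 = +4.7 to (60 − 8)/6 = +8.7.

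**3. Slope.** The post-second-injection model of SAP 6.3.4 was simulated with time, baseline eGFR, and random intercept and slope. One subject was transplanted and then stayed in the study. Visits were at months 1, 2, 3, 6, 9, 12, 15, 18, 21 and 24, with 60 runs per scenario. Assumed: native slope −3 or −5 per year (between-subject SD 1.5), residual SD 1.2, transplant after month 9 or 15, graft eGFR 40 or 60, no dialysis attrition. As a simplification, baseline was placed at the start of the modelled period.

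| n | Slope, graft values removed (SE) | Slope, graft values kept (SE) |
|---|---|---|
| 10 | about −3.0 (0.5) | −1.4 to +0.3 (1.8 to 3.3) |
| 10 | about −4.9 (0.4) | −3.1 to −1.4 (2.1 to 3.5) |
| 6 | about −2.9 (0.6) | −0.2 to +2.5 (3.0 to 5.5) |
| 6 | about −4.8 (0.6) | −1.7 to +1.0 (3.3 to 5.9) |

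In a separate simulation of the whole post-injection period, a subject who left at once with only one end-of-study value kept moved the slope by +0.6 to +2.0 per year.

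**4. Does the Month-24 mean change sign?** In the step 3 runs at n = 10 it went from about −6.0 to between −3.2 and −1.2, or from about −9.7 to between −6.5 and −4.4: upward, but still negative. At n = 6 it became positive only with slope −3 and graft eGFR 60.

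A second set of assumptions also removed subjects at dialysis: decline 4 per year (SD 2), transplant at month 12 after the first injection, graft eGFR 50. The share of simulated trials of 10 in which the mean reversed was 39% with dialysis at eGFR 6, 78% at 8 and 94% at 10. It was 0% with no dialysis attrition. The upward direction is stable; the reversal is not.

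**5. Time to dialysis.** A subject transplanted without dialysis is censored at the last visit and counts as dialysis-free until then. In a composite endpoint that subject would be an event: 1 of 10 (10%) or 1 of 6 (17%).

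**The case against.** The strongest reply is that this is a narrow contingency. It needs a transplant, no earlier dialysis, and a study measurement afterwards, among at most 10 subjects. Protocol 1.1.3 says that most Stage 5 patients receive hemodialysis and that organs are scarce. A transplanted subject may well leave: Protocol 8.6 permits removal, Exclusion 21 covers immunosuppressive agents, and Protocol 5.4 tells the investigator to withdraw a subject whose interest is no longer served. All of this stands as to frequency and the amount of graft data. It does not supply an analysis rule, and one end-of-study value can remain.

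The outlier would also be visible. SAP Section 4 plans median, quartiles, minimum and maximum, 6.3.4 plans subject plots, and the slope is reported with its standard error. That limits the risk of misreading, but the reported mean and slope would still include the graft.

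Three stronger readings are tempting and are not supported:
- A reader might infer that one transplant would turn the mean eGFR change positive. Step 4 shows that this depends on the dialysis threshold and attrition, which the documents do not give.
- A reader might infer that the transplant would go unrecorded. The hospital stay meets the SAE definition (Protocol 8.1.1.1) and would appear in the SAE tables and listings. Time to dialysis is an accurately named endpoint, and SAP Section 10 discloses its addition.
- A reader might infer that removing quality-of-life scores after dialysis is itself an error. It is a prespecified, flagged choice with the scores still listed, and no direction of bias can be shown.

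For ultrasound and scintigraphy, which concern the treated and untreated kidneys, no distortion from the graft has been shown. The change there is for consistency.

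**Conclusion.** The point holds as a gap in wording with a predictable direction. As written, the SAP would keep graft eGFR after a transplant without prior dialysis, provided the subject is measured again. The bias is towards improvement whenever graft eGFR exceeds the native value. Its size is conditional on one such event and on the assumed graft and native values; the leading figure is +2.8 to +5.2 at a visit with n = 10. The slope shift depends further on how long the subject stays.

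The primary endpoint, procedure- or product-related adverse events, is unaffected, and no hypothesis is tested. Severity: minor.

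**What to change.** In SAP 6.2 and 6.3.1 to 6.3.4, define the trigger as the start of dialysis or kidney transplantation, whichever comes first. State that it applies to end-of-study and unscheduled values and to the listing flags, and add a transplantation line to the subject plots. In 6.3.5 keep time to dialysis; optionally, also report time to the first of dialysis or kidney transplantation. No extra quality-of-life table is needed.

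The cost is a few words of text, one further Kaplan-Meier output if the option is taken, and a transplant date drawn from existing records such as the SAE report. Late eGFR figures may be slightly less favourable. If no transplant occurs, the eGFR results do not change.

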### **1.7. Potential Risks**

In general, potential risks associated with the clinical use of REACT can be broadly divided into 3 categories: kidney biopsy, REACT product, and delivery into the recipient kidney. An assessment of potential risks associated with each of these steps is presented in this Section.

At this time, there are no specific warnings or precautions associated with the use of REACT. However, warnings and precautions for the renal biopsy and the percutaneous injection procedure must be considered with use of this product. The risks of renal biopsy have been well characterized in the 100 years that this procedure has been used and developed. Percutaneous needle instrumentation of the kidney has a shorter history.

The risks of renal biopsy and percutaneous needle kidney injection include:

1. Pain in flank / injection/biopsy site
2. Bleeding at injection/biopsy site which may occur around the kidney or anywhere along the needle track and which may be sufficient to entail clinically significant anemia, acute kidney injury (AKI), hematoma, and in the case of subcapsular bleeding, a “Page kidney” and acute hypertension
3. Surgical damage to the kidney from needle injury, as well as injuries of other structures that include connective tissues, bone, and intra-abdominal viscera

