## 9.4. Efficacy Analysis

The primary efficacy endpoint is serial measurements of eGFR obtained at 1, 3, 6, 12, 15, 18, 21, and 24 months after the last REACT injection. GFR will be estimated using the Chronic Kidney Disease Epidemiology Collaboration (CKD-EPI) equation that incorporates both serum creatinine and Cystatin C.

Estimated GFR measured at each time point will be summarized by presenting descriptive statistics of raw data and change from baseline values for each treatment group.

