4.5 Handling of Dropouts or Missing Data

Missing data will remain missing. No imputation of missing data will be performed.

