9. SAMPLE SIZE

Up to 10 subjects who complete screening procedures and satisfy all inclusion and exclusion criteria will be enrolled. Statistical analyses will be primarily descriptive in nature and no statistical hypothesis testing is planned for the study.

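### The SAP's dialysis rules do not separate a temporary course with recovery from maintenance dialysis, so a recovered subject loses all later efficacy values and counts as an event in the dialysis curve

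*SAP*

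**What the plan says.** - **Removal rule.** SAP 6.2: "Measurements taken after dialysis has started will be removed from all efficacy analyses". The sentence recurs for quality of life (6.3.1), ultrasound (6.3.2) and scintigraphy (6.3.3). It sets no condition on duration, reason or recovery. Removed laboratory, quality-of-life and imaging records stay in listings with a notation.
- **Event.** SAP 6.3.5: "Time to dialysis is defined as the time in months from the first REACT injection to the start of dialysis". On censoring: "Subjects who did not start dialysis during the study will be censored as of their last visit date". SAP 10 records that this exploratory endpoint was added in the SAP, and does not define dialysis further.
- **Slope model.** SAP 6.3.4: "Each subject with a minimum of 3 observations during the period of interest will be modeled". This section does not repeat the removal rule. Its subject plots carry a line where dialysis begins, but it does not say whether later points are drawn.
- **Missing values.** SAP 4.5: "Missing data will remain missing. No imputation of missing data will be performed".
- **Foreseeable cause.** Protocol 1.7 describes bleeding from biopsy or needle injection "which may be sufficient to entail clinically significant anemia, acute kidney injury (AKI), hematoma". Protocol 5.1 admits subjects with eGFR 14 to 20 who do not require dialysis.

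**The concern.** A removal rule is sensible while a subject is on dialysis, because creatinine and creatinine-based eGFR then no longer reflect the kidney's own function. That reason ends once the subject is off dialysis and has recovered, but the rule does not end with it.

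Protocol 2 says REACT is meant to delay renal replacement that becomes inevitable in end-stage disease. A short course after a procedural bleed is a different outcome, yet 6.3.5 gives it the same weight.

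The two effects pull apart. If the subject recovers to a lower eGFR, dropping the later values could make the eGFR summaries look better, while the same subject appears as progression in the dialysis curve. With "Up to 10 subjects who complete screening procedures and satisfy all inclusion and exclusion criteria will be enrolled", one such subject is visible in both results.

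**Working it through.** The plan gives no event rate, power or other figure to reproduce here. The check is a reading of the dialysis text, a visit count and a product-limit calculation.

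**1. Search for a qualifier.** No dialysis passage in the protocol or SAP text available contains a temporary/maintenance distinction, a minimum duration or a re-entry rule.

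**2. eGFR points lost.** Protocol 9.4 lists "serial measurements of eGFR obtained at 1, 3, 6, 12, 15, 18, 21, and 24 months after the last REACT injection", which is 8 points. Points kept are those at or before the start of dialysis, with time counted from the last injection:

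| Dialysis starts | Kept | Lost | At least 3 kept? |
|---|---|---|---|
| 1 week | 0 | 8 | no |
| 1.5 months | 1 | 7 | no |
| 3.5 or 5 months | 2 | 6 | no |
| 6.5 months | 3 | 5 | yes |
| 12.5 months | 4 | 4 | yes |

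On this schedule a start before Month 6 leaves at most 2 points (Months 1 and 3). If the last injection was the second, the subject then leaves the post-second-injection slope model. The subject stays in the model for the whole post-injection period if at least 3 values precede dialysis, including those taken between the injections.

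**3. Sensitivity to the schedule.** Protocol Table 2 has 12 visit columns after the last injection: Days 1, 14 and 28, and Months 2, 3, 6, 9, 12, 15, 18, 21 and 24. The marks per test could not be read in the copy used. If eGFR is taken at all 12, fewer than 3 values remain only when dialysis starts before about Day 28. SAP 6.3.4 also admits unscheduled values, which could restore a subject to the model. The loss of all values after the start is the same on either schedule.

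**4. Kaplan-Meier effect.** Assume 10 treated subjects and no censoring before the event. One event gives S = 9/10 = 0.90, a drop of 10 points. Successive events give 0.90, 0.80 and 0.70, so the first quartile (S at or below 0.75) is reached at the third event. Add a transient course at Month 1 to assumed maintenance starts:
- starts at 14 and 20 months: the quartile moves from not reached to 20 months;
- starts at 14, 20 and 24 months: it moves from 24 to 20 months.

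With 8 treated subjects the first drop is 1/8 = 12.5 points.

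**5. Frequency.** The documents give none. Purely as an illustration, with 10 subjects injected twice and an assumed risk p per injection, the chance of at least one such course is 1 − (1 − p)^20. That is 2% at p = 0.1%, 10% at p = 0.5% and 33% at p = 2%. The range is wide because p is unknown, and the point does not rest on it.

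**The case against.** The strongest reply is that little is really lost.

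- **Values survive elsewhere.** Those before dialysis stay in the efficacy analysis. Later ones stay in flagged listings, and SAP 7.3 summarises laboratory parameters by scheduled visit with no dialysis exclusion. This stands. A reader might infer that all the subject's efficacy data are deleted; the documents do not support that.
- **The complication is already reported.** Adverse events are recorded from biopsy to 24 months after the final injection and tabulated by relationship and period (SAP 7.2). The subject plots mark the start of dialysis, and 6.3.5 lists each derived time. This stands, and no new safety reporting is needed. It does not repair the eGFR summaries, slope or curve.
- **The biopsy route is mostly closed.** Inclusion 4 and Exclusion 14 would normally keep a subject dialysed after biopsy from being injected, and these analyses use injected subjects only. This stands. Kidney injury after an injection is the route that remains.
- **The endpoint is named time to dialysis.** A reader might call a temporary course a false event. The SAP never says that only lasting kidney failure counts, so the label is not supported. Counting injection-related dialysis is also the conservative choice, and dropping it would favour the product. This stands and shapes the fix.
- **A duration criterion can mislead.** A 90-day requirement, for instance, could not classify dialysis starting in the last 90 days of follow-up. This stands too.

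**Conclusion.** The concern holds in a limited form. Read literally, the SAP excludes valid values after recovery from its secondary and exploratory efficacy analyses, and gives a temporary course the same standing as maintenance dialysis in 6.3.5.

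For one affected subject the size is up to 8 of 8 eGFR points in Protocol 9.4 if dialysis begins just after the last injection. On that schedule, a start before Month 6 after the second injection also costs the place in the post-second-injection slope model. The dialysis curve drops by about 10 points, assuming 10 treated subjects and no earlier censoring. Applying the removal rule to the slope in 6.3.4 rests on the phrase in 6.2 covering all efficacy analyses, since 6.3.4 does not restate it.

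Two stronger readings are not supported. The loss should not be put at 12 scheduled eGFR visits, because 12 counts visit columns whose test marks could not be read, while Protocol 9.4 names 8 eGFR times. Nor can the event be called likely, because no risk is given. The study is descriptive, and its primary safety endpoint is untouched. The change is still worth making before lock: with so few open-label subjects, deciding how to classify a case after seeing its data would be a result-dependent choice.

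**What to change.** Amend the SAP before database lock. The definitions are for analysis only and change nothing in patient care.

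1. **SAP 6.2 to 6.3.4.** For a subject who comes off dialysis, exclude only values from the first session to a pre-specified interval after the last session, and let later values back in. For a subject who stays on dialysis, keep the present rule. State in 6.3.4 whether the rule governs the slope models and the plotted points.
2. **SAP 6.3.5.** Keep time to any dialysis as written. Add time to maintenance dialysis under a pre-specified duration definition, dated from the start of that course. Count a subject still on dialysis at last contact, death or transplant as an event, so that late starts are not lost.

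The sponsor should choose the interval and the duration; the documents give no basis for a particular figure.

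**Cost.** Dialysis stop dates must be captured, on the CRF or from adverse event records, and one more exploratory summary is produced. A short course that ends in death would count as maintenance under this definition. With so few subjects, the listing will show any such case.
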